history. As part of the inclusion/exclusion criteria, participants will also be asked if they have a history of experiencing severe alcohol withdrawal symptoms and if they are motivated to reduce their drinking in the next 60 days. Penn Alcohol Craving Scale (PACS) consists of 5 self-report items assessing the intensity, duration, and frequency of craving, the ability to resist alcohol, and average level of craving in the past week.¹⁶⁰ Alcohol Abstinence Self-Efficacy Scale (AASE) evaluates an individual's confidence to abstain from drinking according to 4 different scenarios: negative affect, social/positive, physical and other concerns, and withdrawal.¹⁶¹ Drinking Motives Questionnaire Revised (DMQ-R) utilizes self-reported data to measure drinking motives including social, enhancement, coping, and conformity.¹⁷⁹ At baseline, on the quit day, and at the follow-up visit, participants will be asked about their alcohol reduction goal, and any progress toward achieving their chosen alcohol reduction goal.

Smoking Measures. Smoking Use and History will collect information on the onset of regular smoking, smoking behavior (e.g., CPD, years spent smoking, time to first cigarette in the morning), smoking history (e.g., age smoked first cigarette), quit attempts, other household smokers, number of friends/family who smoke, and use of other tobacco products (e.g., e-cigarettes, cigars, hookah, snus). Participants will also be asked if they are motivated to quit smoking in the next 60 days, as part of the inclusion/exclusion criteria. Brief Wisconsin Inventory of Smoking Motives (WISDM) is a 37-item self-report measure used to assess nicotine dependence as a multi-dimensional construct via 11 different smoking motives.¹⁶² Wisconsin Smoking Withdrawal Scale (WSWS) includes 7 subscales assessing nicotine withdrawal symptoms according to 28 items.¹⁶³ Self-efficacy Scale - Smoking is a 20-item self-report measure that determines an individual's level of confidence for not smoking in positive/social situations, negative affect situations, and out of habit.¹⁶⁴

Mindfulness Measures. Five Facet Mindfulness Questionnaire (FFMQ) is a 39-item Likert-scale measure assessing 5 facets of trait mindfulness.⁴⁰ Toronto Mindfulness Scale (TMS) is a 13-item Likert-scale self-report measure of state mindfulness.⁴¹ The TMS yields two factors: Curiosity and Decentering.

Negative Affect/Depression/Stress/Anxiety Measures. Center for Epidemiological Studies Depression Scale (CESD) is a 20-item self-report questionnaire that assesses depressive symptoms experienced within the past week.¹⁶⁵ Distress Tolerance Scale (DTS) is a 15-item, Likert-scale self-report measure of an individual's perception of his/her own emotional distress tolerance.¹⁶⁶ Perceived Stress Scale (PSS) is a widely used self-report measure that assesses the degree to which participants find their lives to be stressful.¹⁶⁷ Positive and Negative Affect Scale (PANAS) is a 20-item self-report Likert-scale measure that assesses an individual's positive and negative affect at a given point in time.¹⁶⁸

Alcohol and Smoking Outcomes. Alcohol Use. The Timeline Followback (TLFB)¹⁷¹⁻¹⁷³ will be used to determine daily, recent alcohol use via retrospective self-report. A calendar is provided to participants, and they indicate any key events that occurred on certain dates to aid their memory. Participants then indicate how much alcohol they drank on each day. The TLFB has been widely used, evaluated, and has strong psychometric properties.¹⁷¹⁻¹⁷³ The TLFB will collect alcohol use from the past 4 weeks at the phone screen. The TLFB will be administered at each of the following visits and will ask participants to report their use since the last time they completed the TLFB: before visits 4 and 8, and at the 8-week and 16-week follow-up. From the TLFB, the primary outcome measure derived will be the percent of heavy drinking days (defined as: on a single occasion, ≥ 5 drinks for men and ≥ 4 drinks for women). Other alcohol use outcomes, such as percent days' abstinent and alcoholic drinks per drinking day, will also be derived.

Smoking Abstinence. To determine smoking abstinence, we will use the 7-day point prevalence, which is a combination of a self-report of no smoking in the last 7 days, combined with a biochemical verification of abstinence via saliva cotinine. Participants who report abstinence will be mailed a saliva cotinine kit to confirm abstinence at their 16-week follow-up call. The TLFB will be used to collect tobacco use throughout the study, and the schedule will mimic that used to collect alcohol use.

G. Data Management and Statistical Considerations for Study 2

To ensure participant confidentiality, no unique identifiers will be recorded into the dataset to be analyzed. Data will be collected via REDCap. The entered and reviewed data will be transferred monthly to a SPSS database.¹⁷⁴

Sample Size. Randomizing 64 participants to MBRP-SA and CBT will provide sufficient data for assessing feasibility of the RCT, based on existing recommendations in the literature for sample size estimates in feasibility studies.^{175,176} A full set of statistical analyses focusing on treatment differences will be performed as part of the feasibility assessment. However, the sample size will not be sufficient for detecting treatment differences for anything less than large effect sizes (e.g., Cohen's $d \geq .72$) for simple, two-group comparisons of a continuous variable with $\alpha=.05$, power $\geq .80$, and a two-tailed test. Binary variables assessed under the same testing conditions would require an $OR \geq 5.95$.

Data Analysis Overview. Analyses will be conducted with SPSS and SAS version 9.4¹⁷⁴ and Mplus Version 7.¹⁷⁷ Descriptive statistics of demographics, smoking history, and alcohol history variables will be calculated and group comparisons will be performed. Descriptive statistics of all study measures (i.e., proximal and distal measures of alcohol use and smoking) will be calculated. Although underpowered to detect small- or medium sized sex differences, all analyses will examine sex as a covariate. Furthermore, analyses will include treatment group (i.e., each subset of participants who are treated with MBRP-SA or CBT together) when the intraclass correlation coefficient is > 0.10 .

Aim 2 - Evaluate benchmarks regarding feasibility and acceptability. Feasibility will be assessed by the multiple indices described in Table 5. Each index will either be compared to published norms (e.g., CSQ) or our prior experience with clinical trials. We expect to recruit adequate numbers of eligible participants during the study timeframe with efficient cost expenditures, retain at least 80% through the end of treatment, and retain at least 70% through the end of the study. Treatment acceptance and satisfaction are expected to be 80% or higher, and participants are expected to comply with treatment requirements. The team will determine whether corrective actions for future studies are needed when an index suggests underperformance. Evaluation of all indices will inform and guide modification prior to the proposal of a full-scale RCT.

Aim 3 - Collect and examine descriptive data on proximal and distal variables associated with alcohol use and smoking. Descriptive statistics of proximal measures (e.g., negative affect, self-efficacy) will be presented in figures to review change over time and treatment differences. Generalized estimating equations (GEE) will be used to fit population-averaged models with the main variables of treatment, time, and their interaction. An AR(1) working correlation matrix will be used with $r=.70$. Covariates and potential confounding variables will be included, as warranted. This approach preserves data for analysis by avoiding listwise deletion of observations when at least one dependent variable was observed. Qualitative analyses (e.g., thematic analysis) may also be conducted on aspects of the treatment process.

A similar approach to analysis will be taken for the primary outcomes (the distal measures). TLFB will be used to derive a measure of heavy alcohol use and the 7-day point prevalence will be created for smoking abstinence at five targeted 1-week periods prior to a session: start of treatment (week -4), quit date (week 0), end of treatment (week +3), and two follow-ups (week +8 and week +16). Descriptive statistics will be presented in figures. GEE with an AR(1) working correlation matrix ($r=.60$) will be used to assess the effects of treatment, time (-4, 0, +3, +8, +16), and their interaction on the primary outcome measures. Means, percentages, and 95% confidence intervals will provide useful guidance as we determine sample sizes for a full-scale RCT. There is not adequate power to detect small- to medium-sized treatment group differences given the sample size. However, we would interpret any within-subject decreases in the number of heavy drinking days from pre- to post-treatment and/or any within-subject increases in smoking abstinence as evidence that the MBRP-SA intervention may be beneficial for these two problematic health behaviors. Given the small sample size, these changes are not likely to be significant. However, sample means and standard deviations will provide valuable data for

estimating sample size in a large-scale RCT. Changes in craving, self-efficacy, and general use of alcohol and smoking will also be examined as proximal outcomes that will also inform the development of a large-scale trial.

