MBRP-SA Development. The primary adaptation for MBRP-SA will be to tailor some the session content and discussions to smoking cessation and alcohol use. These changes will be primarily guided by the existing literature (e.g., studies on mindfulness-based treatments for smoking cessation) and the experience/knowledge of the investigative team. It should be noted that MBRP already addresses some of the primary underlying mechanisms of smoking cessation and reduced alcohol use (e.g., managing negative affect and craving) and that the extant literature indicates that key behavior modification constructs (e.g., self-efficacy) are impacted by mindfulness.^{45,50,67,76} Therefore, we will not modify the core components of MBRP, but instead supplement the existing protocol with content unique to smoking and alcohol use.

Content Modifications. Content modifications listed here fall into 3 categories: smoking-specific, alcohol-specific, and co-use. Given MBRP has already demonstrated efficacy for reduced alcohol use, most of these modifications focus on smoking and co-use content. Modifications are based on the existing literature, ability of content to address underlying behavior-change mechanisms (e.g., motivation) and Co-I [name] experience developing and testing a mindfulness-based cessation intervention.⁵⁸ **SMOKING-SPECIFIC: Quit date.** Research regarding smoking cessation indicates that motivation can be enhanced by setting a specific quit date.¹⁴² Therefore, MBRP-SA will set the smoking quit date at Session 5, which is supported by existing mindfulness-based cessation treatments (e.g., ⁵⁸). This permits time for individuals to develop their mindfulness practice (Sessions 1-4) while still providing ongoing support for 3 weeks after the quit day. **Losing a friend.** Many smokers report that smoking a cigarette represents a type of "friendship" and that quitting smoking is like losing a close friend.¹⁴³⁻¹⁴⁵ MBRP-SA will acknowledge and process this type of cognition in Session 3. **Diet and Weight Gain.** Many individuals endorse motivation to continue smoking for weight control purposes,¹⁴⁴ and therefore we will include information on this topic in Session 3. **Nicotine Patch.** Current guidelines for smoking cessation indicate that when provided with a combination of nicotine replacement therapy and counseling, chances of success are greatest.¹⁴² Thus, participants will be

[figure not shown]

Figure 3. Treatment Development Flow

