treatment, concerns about logistically attending sessions, and appealing features of the treatment). Step five will include revising the treatment procedures and content based on the results from each cohort of development testing. Table 2 provides an overview of the timeline for Study 1.

Statistical Considerations. The primary goal of Study 1 is to develop MBRP-SA. Qualitative analysis of focus group will be the primary form of evaluation. The focus group will be audio-recorded and verbatim transcripts created for content analysis.¹⁵⁰ Using hand coding, the goal will be to identify key themes/textual units related to mindfulness and response to the treatment. Results from the qualitative interviews will be analyzed using the interview transcripts and content analysis. Content analysis will be conducted using an “intuitive” or “immersion/crystallizing” analysis plan, whereby the researcher reviews all data and pulls out those aspects most relevant to the research questions.¹⁵¹ The research team will identify key themes as they read through the interview transcripts. Descriptive statistics of quantitative measures will supplement the qualitative analysis. These may provide information for identifying aspects of implementation that require change prior to the feasibility study (Study 2).

Aim 2.

*Note: All procedures reported for Aim 2 will be conducted remotely, primarily via zoom and phone calls (but also via mailouts, emails, and text messages as appropriate). Group treatment sessions (MBRP-SA and CBT) will be conducted via zoom.

Project Overview. The primary goal of Study 2 is to measure benchmarks regarding the feasibility and acceptability of the MBRP-SA protocol created in Study 1. Participants (N=64) will be randomized to either MBRP-SA or CBT and tracked from 5 weeks pre-quit through 16 weeks post-quit. The first follow-up appointment will be a phone call scheduled at 8 weeks post-cessation (± 5 days). The second follow-up appointment will be a phone call scheduled at 16 weeks post-cessation (± 5 days). Table 4 provides a timeline of all procedures and assessments. Details are presented in the subsequent sections. Administering the battery of assessments below according to this timeline mimics the procedures for a future, large-scale R01 efficacy trial and will allow for the evaluation of feasibility for completing all procedures.

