Treatment Overview. All participants will receive nicotine replacement therapy (NRT) and either MBRP-SA or CBT. Table 4 provides an overview of all treatment and follow-up visits.

NRT. The nicotine transdermal patch is the most widely used pharmacotherapy and the Treating Tobacco Dependence Clinical Practice Guideline has identified it as frontline therapy.¹⁴² The patch is safe, tolerable, and available over-the-counter. Patch therapy for participants who smoke >10 CPD will consist of 6 weeks of 21 mg patches and 2 weeks of 14 mg patches. Patch therapy for participants who smoke 5-10 CPD will consist of 6 weeks of 14 mg patches and 2 weeks of 7 mg patches. Patch dispensation will occur at weekly treatment visits. Participants receive only the number of patches needed to last until the next visit plus several extra patches should one fall off, become torn, etc, or should the visit be delayed. Based on our previous research, compliance is improved when participants are provided with only enough patches to last until the subsequent visit. A reduction in dosage or cessation of the patch regimen will be implemented for any participants who show signs of being on too high of a dose, which is expected for very few participants since blood nicotine levels are usually much lower on the patch than while smoking. Note that for Aim 2, patches will be mailed each week.

MBRP-SA and CBT. MBRP-SA was already described above. CBT is a well-established and commonly used treatment for substance use behaviors that primarily utilizes a problem solving and coping skills approach rooted in relapse prevention theory,¹⁵² combined with standards from the Guideline.¹⁴² Session content will generally follow the manual used in the original MBRP RCT⁶⁴, the MBAT RCT⁵⁸, and standards from the Guideline (e.g., setting a quit date, providing NRT).¹⁴² CBT will consist of 8 sessions (2 hours each), with 8-10 participants in each group. Thus, participants in both MBRP-SA and CBT will be matched on treatment contact time. All treatment activities focus on promoting/maintaining smoking abstinence and reducing drinking, with specific treatment objectives for each session. Participants will receive weekly emails that outline the group session as well as include relevant links and attached handouts for their review. Participants will also receive referrals for mental health and substance use at the end of treatment.

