3.4 Investigator Study Files

Research records for patients on this study are the responsibility of the investigator. They will be available for review by the sponsors of the trial, health care personnel involved in this study, the IRB, DHHS, and the FDA.

Sources of Materials

Data collected from participants for research purposes include a saliva testing for Cotinine (a nicotine metabolite) and self-report measures and interview data that collect demographic, medical history, psychiatric symptoms, smoking-related information, alcohol-use information, and questions about personality traits and current affective and cognitive states. Data will be collected electronically via REDCap. The treatment sessions for the MBRP-SA group involve mindfulness (meditation) practice that is tailored to smoking cessation and reducing alcohol use. The treatment sessions for the CBT group involve coping and reappraisal skill training that is tailored to smoking cessation and reducing alcohol use. Participants will be asked about the feasibility and acceptability of the treatments, in addition to monitoring their homework practice each week.

Potential Risks

Minimal risks are anticipated for this study. Data including self-report, interview (psychological and medical), and biological samples (e.g., saliva) involve risk of breaches in confidentiality. Although everyone will be asked to keep the information shared during the group sessions confidential and to maintain anonymity outside of sessions, a breach of confidentiality is always possible. Participants will always be given the option to refuse to answer any questions on the measures that may be distressing. Successful abstinence may cause irritability, anxiety, general distress and difficulty concentrating. The nicotine patch that participants will wear beginning on the quit date will be the appropriate dose for their level of smoking, and the patch should aid in the management of withdrawal symptoms. The nicotine patch and smoking cessation counseling have been shown to be safe and effective for smokers attempting to quit. However, side effects to the patch may occur and include skin irritation/ rash, nausea, dizziness, dry mouth, diarrhea, nervousness, headache, vivid dreams or sleep disturbances, irritability, and irregular heartbeat.

Protections Against Risks

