We believe that this study poses minimal risks. Potential side effects from the nicotine patch will be closely monitored by study staff and the PI. Participants will be told of potential allergic reactions and side effects in response to the patch and nicotine side effects, and also told that they are free to remove the patch at any point in time. Should participants feel any possible side effects, they will be advised to discontinue the patch, and also told that they can call the PI and study staff. Counseling will be provided by clinicians who have received ample training regarding ethical principles of counseling. Emergency procedures will be in place should any psychiatric emergency arise during the screening and/or treatment processes. Although this is likely to be very rare, all study personnel and counselors will be trained in these procedures. Should a person drop-out of treatment early, community referrals for smoking, alcohol use, and mental health services will be provided. To ensure that any data (e.g., psychological, medical, personal) collected from this study remains confidential, hardcopy and electronic storage of data will be identified by participant number, so that data will not be directly associative with names. Association between participant names and numbers will not be kept in the same location as the data. Electronic files will be protected by password access, and hard copies will remain in a locked cabinet when not in use. Saliva samples will be discarded and have no identifying information after analyses.

Any electronic data will be stored on internal drives and in password-protected files without participant identifiers. Storage of any paper files will be kept in locked filing cabinets. Only study personnel will have access to these files.

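### The patch course lasts 8 weeks, but Table 4 ends sessions and dispensing at week 3: 30 to 35 of 56 patch days have no scheduled contact, and the supply statements do not fit together

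*Combined protocol and SAP*

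**What the plan says.** **Course length.** Under Aim 2, Treatment Overview, NRT, the regimen for more than 10 cigarettes per day "will consist of 6 weeks of 21 mg patches and 2 weeks of 14 mg patches". The regimen for 5 to 10 per day "will consist of 6 weeks of 14 mg patches and 2 weeks of 7 mg patches".

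**Start.** Section 3.4 (Potential Risks) refers to "The nicotine patch that participants will wear beginning on the quit date". The content modifications state that "MBRP-SA will set the smoking quit date at Session 5". Table 4 labels Session 5 as week 0, Quit Day, for both arms.

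**Dispensing.** The NRT paragraph ties dispensing to the weekly treatment visits and sets the quantity: "Participants receive only the number of patches needed to last until the next visit plus several extra patches". It justifies this by saying that small supplies improve compliance. It ends: "Note that for Aim 2, patches will be mailed each week". Table 4 marks dispensation at weeks -1, 0, 1, 2 and 3 only. Session 8 is at week 3.

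**Next contact.** The Aim 2 Project Overview places the first follow-up at a phone call 8 weeks after the quit date, with a window of 5 days either side. The following one is at 16 weeks.

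**Safety monitoring.** Section 3.4 (Protections Against Risks) promises: "Potential side effects from the nicotine patch will be closely monitored by study staff and the PI". It also says that participants will be told about side effects and may call the study team. Section 6.5 has staff observing participants during treatment sessions, reporting adverse events to the principal investigator (PI) and recording them in a named database. Table 4 lists no side-effect or adverse-event item in any column.

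**The concern.** The nicotine patch is the only drug in the trial. Its stated course outlasts the treatment sessions by five weeks, and the one safety activity with a stated time, observation during sessions, stops when they do. After week 3 the documents name no occasion on which anyone asks about patch side effects. The NRT paragraph also provides for reducing or stopping the patch when a participant shows signs of too high a dose, which depends on someone seeing those signs.

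Two things are at stake. First, adverse-event data from more than half of the patch exposure could depend on participants calling in, which makes any summary for NIH harder to interpret. Second, the schedule does not make clear what patch supply participants receive after week 3. The week-8 and week-16 outcomes are meant to guide sample sizes for a full-scale trial, and Aim 2 is meant to rehearse that trial's procedures, so an undefined supply and monitoring schedule could carry over.

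**Working it through.** The documents give no total for patch days or for days without contact, so there is no stated figure to reproduce. The check is calendar arithmetic with the quit date as day 0.

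**Inputs.** Course of 6 + 2 weeks (NRT paragraph); start at week 0 (section 3.4, Table 4); last session and last marked dispensation at week 3 (Table 4); call at week 8 ± 5 days (Aim 2 Project Overview).

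**Step 1: the course.** 6 + 2 = 8 weeks; 8 × 7 = 56 patch days, days 0 to 55. The strength changes on day 6 × 7 = 42.

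**Step 2: after the last session.** Session 8 is on day 3 × 7 = 21. Remaining patch days: 56 - 21 = 35 (days 21 to 55), or 35/7 = 5.0 weeks and 35/56 = 62.5% of the course. The strength change comes 42 - 21 = 21 days after Session 8.

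**Step 3: the call window.** 8 × 7 = 56; 56 ± 5 gives days 51 to 61.

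| Call on day | Patch days from Session 8 to the call | Weeks | Days from strength change to call | Patch days left after call |
|---|---|---|---|---|
| 51 | 51 - 21 = 30 | 4.3 | 9 | 5 |
| 56 | 56 - 21 = 35 | 5.0 | 14 | 0 |
| 61 | 35 (course ends on day 55) | 5.0 | 19 | 0 |

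The gap is therefore 30 to 35 of 56 patch days (53.6% to 62.5%), and the strength change falls inside it wherever the call lands.

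**Step 4: supply after week 3.** The answer depends on whether the week -1 supply covers week 0. The Aim 1 text, which has patches handed out at Session 4 for use from Session 5, suggests that it does.

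- *Weekly mailing continues to the end of the course.* The course is covered, but Table 4 omits every mailing after week 3.
- *One week-3 parcel lasts to the week-8 call.* If the week -1 supply covers week 0, the first four supplies cover days 0 to 27. The parcel then holds 56 - 28 = 28 patches (14 of the first strength, 14 of the second). If the week -1 supply does not count, the parcel holds 56 - 21 = 35 (21 and 14). Either way it is about 4 to 5 weeks of two strengths, against the stated reason for small supplies.
- *Only week-sized supplies go out on the Table 4 dates.* The total is 5 × 7 = 35 or 4 × 7 = 28 of 56 patches, plus the extras.

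No reading satisfies the 8-week course, the weekly mailing, the small-supply rationale and the Table 4 row together.

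**Step 5: monitoring, side by side.** Section 3.4 makes a promise with no timing. Section 6.5 times observation to treatment sessions, which end on day 21. Table 4's week-8 column holds questionnaires, alcohol goals and the Timeline Followback, with nothing on patch side effects. Between days 21 and 51 at the earliest, the only stated route is a call from the participant.

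**The case against.** The strongest reply on supply is that the quantity rule already resolves it. If patches must last until the next visit, and the contact after Session 8 is the week-8 call, then one week-3 parcel completes the course, and weekly mailing is simply the remote form of the weekly visits. That reading is available. A reader might infer that participants run out near week 4, but that follows only if week-sized supplies are sent on the Table 4 dates and the week -1 supply is ignored. The documents do not establish it. What remains is that the resolving reading conflicts with the paragraph's own rationale and that weekly mailing has no stated end.

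On safety, a general promise and a silent table do not strictly contradict each other. Table 4 also leaves out the homework questionnaire, the dropout interview and the in-depth interviews, so it is not a full list of procedures. Section 6.5 puts no time limit on adverse-event capture, section 3.2 has adverse events discussed at weekly meetings, and participants are told about side effects and may call. It would therefore be too strong to say that no safety monitoring is planned after week 3, or that the NIH summary must rest mainly on the first three patch weeks. The supportable statement is that no contact is scheduled and no question is specified.

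Two further points temper the concern. The protocol describes the patch as safe, tolerable and available over the counter, and in both regimens the strength change is to a lower strength. The day-51 call is also the edge of the window; on the nominal date the course has just ended.

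**Conclusion.** The point holds in this form. On the stated schedule, 30 to 35 of 56 patch days (4.3 to 5.0 weeks), including the strength change at day 42, pass with no scheduled contact. No side-effect or adverse-event item appears in Table 4 at any time point, including the 8-week call. The statements on course length, quantity, mailing and dispensing dates do not fit together after week 3.

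This rests on three assumptions: the patch starts on day 0 and is worn for the full stated course; sessions and calls follow the nominal calendar apart from the ± 5 day window; and the Table 4 columns are read correctly. The dispensation row does agree with the text placing the first supply at Session 4. The patch counts (28 to 35) are ranges because the documents do not say what the week -1 supply covers.

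The documents do not show that participants will go without patches, that adverse events after week 3 will be missed, or that the minimal-risk judgement is wrong. The change is worth making because it is cheap and improves the safety data. It does not undermine the feasibility benchmarks.

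**What to change.** 1. Reconcile the NRT paragraph (course length, quantity rule, weekly mailing) with the Table 4 dispensation row, so that one schedule can be read from both. The sponsor decides which governs; no dose, stopping or dispensing rule is proposed here.
2. Reconcile sections 3.4 and 6.5 with Table 4 by adding a short side-effect and adverse-event question, worded identically in both arms and covering the patch period including weeks 3 to 8. Use channels already in the protocol: REDCap, text messages and the existing 8-week call. The sponsor chooses the frequency. Replies go to the PI and into the adverse-event database already named.

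**Cost.** Protocol wording, one short form, slight participant burden, and staff time to review and follow up replies. For scale only, one message a week for five weeks would be 5 × 64 = 320 messages across the trial. No additional visit is needed.
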